7.3 Lost to Follow up

A participant will be considered lost to follow-up if he repeatedly fails to return for scheduled visits and is unable to be contacted by the study site.

The following actions must be taken if a participant fails to return to the clinic for a required study visit:

- The site must attempt to contact the participant and reschedule the missed visit as soon as possible and counsel the participant on the importance of maintaining the assigned visit schedule and ascertain whether or not the participant wishes to and/or should continue in the study.
- Before a participant is deemed lost to follow up, the investigator or designee must make every effort to regain contact with the participant (where possible, 3 telephone calls and, if necessary, a certified letter to the participant's last known mailing address or local equivalent methods). These contact attempts should be documented in the participant's medical record.
- Should the participant continue to be unreachable, he/she will be considered lost to follow-up.

Discontinuation of specific sites or of the study as a whole are handled as part of Appendix 1 (Section 10.1).

8. Study Assessments and Procedures

- Study procedures and their timing are summarized in the SoA (Section 1.3). Protocol waivers or exemptions are not allowed.
- Immediate safety concerns should be discussed with the sponsor immediately upon occurrence or awareness to determine if the participant should continue or discontinue study intervention.
- Adherence to the study design requirements, including those specified in the SoA (Section 1.3), is essential and required for study conduct.
- All screening evaluations must be completed and reviewed to confirm that potential participants meet all eligibility criteria. The investigator will maintain a screening log to record details of all participants screened and to confirm eligibility or record reasons for screening failure, as applicable.

- Procedures conducted as part of the participant's routine clinical management (e.g., blood count) and obtained before signing of the ICF may be utilized for screening or baseline purposes provided the procedures met the protocol-specified criteria and were performed within the time frame defined in the SoA (Section 1.3).

8.1 Efficacy Assessments

Assessments specific to tumor burden will not be collected in this study. Participants will be followed for survival to assess the 1-year survival rate.

8.2 Safety Assessments

Planned time points for all safety assessments are provided in the SoA in Section 1.3.

Safety assessments in this study are AEs, as recorded by the investigator. Descriptive summary tables will be presented for all safety parameters by each treatment arm.

All AEs will be coded using the Medical Dictionary for Regulatory Activities (MedDRA) coding system and graded using NCI-CTCAE version 5.0. A TEAE is defined as any event arising or worsening after start of study drug administration until 30 days after the last study drug intake.

Fatigue, cognitive function and depression will be assessed as described below.

Other AEs of interest including fractures, falls, fractures, and hypothyroidism will be collected with specific questions on CRF.

Study assessments for physical ability and cognitive function are described in [Table 8–1](#).

Table 8–1: Study Assessments for Physical Ability and Cognitive Function

Test	Description	Possible range of score	MCID / RCI from baseline
Physical ability tests			
Timed Up & Go (TUG)	The TUG test is used to assess a person's mobility and requires both static and dynamic balance. It uses the time that a person takes to rise from a chair, walk three meters, turn around, walk back to the chair, and sit down. Where possible, TUG time is to be measured by independent blinded assessors.	>1second	1 second (Davies et al. 2016)
Short Physical Performance Battery (SPPB)	The SPPB is a group of measures that combines the results of the gait speed, chair stand and balance tests.	0–12 points	0.5 points (Davies et al. 2016)
Cognitive Tests			
Hopkins Verbal Learning Test-Revised Total Recall (HVLTR TR)	The HVLTR is a learning and memory test, in which the participant is asked to learn and recall a list of 12 words over 3 trials.	0–36 words	±5 words (Wefel et al. 2011)
Hopkins Verbal Learning Test-Revised Delayed Recall (HVLTR DR)	Spontaneous recall is assessed before and after a delay.	0–12 words	±3 words (Wefel et al. 2011)
Hopkins Verbal Learning Test-Revised Delayed Recognition (HVLTR RECOG)	Recognition discriminability is also assessed after a delay. Four alternate versions of the test are used to minimize practice effects over time.	-12–+12 words	±2 words (Wefel et al. 2011)
Trail Making Test (TMT) Part A (TMTA) Part B (TMTB)	The TMT Part A (TMTA) assesses visual scanning and motor tracking requiring focused attention. Participants are required to sequentially connect numbered dots in ascending order that are randomly scattered across the test page. Part B (TMTB) includes a divided attention component requiring mental flexibility (i.e., executive function). On this subtest, dots with numbers and	1–2750 seconds 1–3750 seconds	±12 seconds ±26 seconds (Wefel et al. 2011)

Test	Description	Possible range of score	MCID / RCI from baseline
	
letters are randomly scattered on the test page. Participants are required to alternate between connecting numbers and letters in an ascending sequential order.
 
Both tests require the participants to complete the sequence as fast as possible. TMTA is discontinued after 3 minutes and TMTB is discontinued after 5 minutes for participants who have difficulty in order to reduce participant burden.
		
Controlled Oral Word Association (COWA)	The COWA test assesses lexical fluency. Given a specific letter of the alphabet, participants are required to produce as many words as possible that begin with that letter. There are two alternate forms of the COWA, each with three unique letter exemplars.	0 – unlimited words	±12 words (Wefel et al. 2011)
Cognitive tests – Patient-reported outcomes			
Functional Assessment of Cancer Therapy-Cognitive (FACT-Cog)	The FACT-Cog questionnaire was developed to assess perceived cognitive function and impact on quality of life (QOL) in cancer patients. It is a patient-reported outcome measure used to assess cognitive function in patients undergoing cancer therapy.	0–28 points	6.9-10.6 points (Cheung et al. 2014, Costa et al. 2018)

COWA = Controlled Oral Word Association; FACT-Cog = Functional Assessment of Cancer Therapy-Cognitive; HVLTR DR = Hopkins Verbal Learning Test-Revised Delayed Recall; HVLTR RECOG = Hopkins Verbal Learning Test-Revised Delayed Recognition; HVLTR TR = Hopkins Verbal Learning Test-Revised Total Recall; MCID = minimal clinically important difference; QOL = quality of life; RCI = reliable change index; SPPB = Short Physical Performance Battery; TMTA/TMTB = Trail Making Test Part A/B; TUG = Timed up & Go

In addition, fatigue will be assessed using BFI. BFI is a validated tool and consists of three questions assessing the severity of fatigue and six questions assessing the impact of fatigue on the participant's mood, social functioning and physical functioning. The BFI is a 9-item scale developed to assess subjective fatigue. Each question is asked in relation to the last 24 hours and is scored on an 11-point numerical rating scale, with higher scores indicating greater fatigue and interference with functionality. The first three questions measure fatigue severity at current, usual, and worst levels from 0 to 10, with 0 indicating "no fatigue," and 10 indicating "as bad as you can imagine". The following six questions assess fatigue interference with daily activities including general activity, mood, walking ability, normal work (both inside and outside the home), relations with other people, and enjoyment of life. Response options range from 0 to 10 with 0 indicating "does not interfere" and 10 indicating "completely interferes." Higher scores on the BFI correspond to greater self-reported levels of fatigue.

Depression will be assessed using PHQ-9. It is a self-administered version of the Primary Care Evaluation of Mental Disorders (PRIME-MD) diagnostic instrument for common mental

disorders. The PHQ-9 is the depression module, which scores each of the 9 Diagnostic and Statistical Manual of Mental Disorders (DSM-IV) criteria as “0” (not at all) to “3” (nearly every day) (Kroenke et al. 2001). As a severity measure, the PHQ-9 score can range from 0 to 27, since each of the 9 items can be scored from 0 (not at all) to 3 (nearly every day). Major depression is diagnosed if 5 or more of the 9 depressive symptom criteria have been present at least “more than half the days” in the past 2 weeks, and 1 of the symptoms is depressed mood or anhedonia. Other depression is diagnosed if 2, 3, or 4 depressive symptoms have been present at least “more than half the days” in the past 2 weeks, and 1 of the symptoms is depressed mood or anhedonia. One of the 9 symptom criteria (“thoughts that you would be better off dead or of hurting yourself in some way”) counts if present at all, regardless of duration.

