1.2 Schema

Figure 1–1: Study Periods

CRPC = castration-resistant prostate cancer; N = number of participants; R = randomization
Randomization will be stratified by age (<75 vs ≥75 years).

Table 1–1 Schedule of Activities for the Lead-in Phase (darolutamide)												
Assessment	Screening	Intervention + Observation Period								End of treatment visit (30 days after last dose) ^m	Survival follow-up ^{l,n}	
		Week 1 Day 1 ⁱ	Week 4 ^j	Week 8	Week 12	Week 24	Week 38	Week 52	from Week 53: Active follow up every 3 months ^{k,l}			
Time window allowed	within 21 days prior to first dose		± 7 days	± 7 days	± 7 days	± 7 days	± 14 days	± 7 days	± 1 month	+ 1 month	± 1 month	
Treatment dispensing / accountability		X	←=====→									
AE review ^b		←=====→										
AEs of interest review, including fall ^c		←=====→										
Timed Up and Go assessment (TUG) ^d	X ^h	X ^h			X	X		X	X			
Short Physical Performance Battery (SPPB) ^d		X			X	X		X	X			
Accelerometry assessment ^e	X				X	X		X	X			
Cognitive function ^f		X				X		X	X			
Brief Fatigue Inventory (BFI) ^g		X	X	X	X	X		X				
Patient Health Questionnaire (PHQ-9)		X	X	X	X	X		X	X			
Survival status											X	

X = measure/action to be performed at the time point indicated

←=====→ = measure/action to be performed continually during the time period indicated

AE = adverse event; BFI = Brief Fatigue Inventory; COWA = Controlled Oral Word Association; CRF = case report form; HVLTR = Hopkins Verbal Learning Test - Revised; PHQ-9 = Patient health questionnaire-9; PSA = prostate-specific antigen; SPPB = Short Physical Performance Battery; TMT = Trail Making Test; TUG = Timed Up and Go

- a PSA will be assessed at the same time as other laboratory assessments. A time window of ± 14 days is allowed for laboratory and PSA assessments.
- b Including survival, pain, radiographic progression, metastases, and skeletal events
- c AEs of interest are fractures, falls, and hypothyroidism
- d Physical function tests include SPPB and the TUG assessment.
- e Accelerometry assessment will require the participant to wear an accelerometry device on the wrist or hip for a minimum of 7 days at each time point. The first accelerometry assessment is to be performed before the first dose (i.e. during screening).
- f Cognitive function tests include the HVLTR, TMT, and COWA, as well as the patient-reported outcome questionnaire FACT-Cog.

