Administration of 600 mg darolutamide bid over 4 days prior to administration of a single dose of 5 mg rosuvastatin, a BCRP substrate, together with food resulted in a 5.2-fold increase in mean exposure [AUC(0-24)] of rosuvastatin and a 4.9-fold increase in C_{max} . These results indicate that co-administration of darolutamide can also increase the plasma concentrations of other concomitant BCRP substrates (e.g. methotrexate, sulfasalazine, fluvastatin, atorvastatin). Therefore, participants should be closely monitored for signs and symptoms of increased exposure to BCRP substrates. Dose modification of BCRP substrates should be considered based on the prescriber information.

For participants receiving enzalutamide in the study, the use of concomitant medications should follow the prescriber information for enzalutamide ([XTANDI™ Prescribing information](#)).

Prohibited concomitant medications and treatments

Concomitant treatment with another systemic antineoplastic therapy or another investigational medicinal product is prohibited with the exception of ADT throughout the study.

Initiation of the following medications during the study treatment period is prohibited:

- any investigational medicinal product

- radiopharmaceuticals
- radium-223
- immunotherapy (e.g. sipuleucel-T)
- cytotoxic chemotherapy
- apalutamide, bicalutamide, flutamide, nilutamide
- abiraterone acetate, TAK-700, or other CYP17 inhibitors
- systemic ketoconazole as antineoplastic treatment for prostate cancer
- ADT switch to LHRH agonist
- another systemic antineoplastic therapy may be initiated no sooner than 7 days after the last dose of study intervention
- any medication that would affect the assessment of physical or cognitive function

For prohibited prior therapy, please refer to the exclusion criteria in Section 5.2.

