8.3.1 Time Period and Frequency for Collecting AE and SAE Information

An AE (irrespective of causal relationship) not completely resolved at the end of the pre-defined collection period must be followed up until resolution (defined as chronicity, baseline grade or complete resolution) or until the investigator considers the event will not improve further.

All SAEs will be collected from the signing of the informed consent form (ICF) until 30 days after the last dose, at the time points specified in the SoA (Section 1.3).

All AEs will be collected from the signing of the ICF until the follow-up visit(s) at the time points specified in the SoA (Section 1.3).

Medical occurrences that begin before obtaining informed consent will be recorded on the medical history section of the case report form (CRF).

Medical occurrences that begin before the start of study intervention but after obtaining informed consent will be recorded on the AE section of the CRF.

Medical occurrences that started before but deteriorated after obtaining informed consent will be recorded as AEs.

All SAEs will be recorded and reported to the sponsor or designee immediately and under no circumstance should this exceed 24 hours, as indicated in Appendix 3 (Section 10.3). The investigator will submit any updated SAE data to the sponsor within 24 hours of it being available.

Investigators are not obligated to actively seek AE or SAE after conclusion of the study participation. However, if the investigator learns of any SAE, including a death, at any time after a participant has been discharged from the study, and he/she considers the event to be reasonably related to the study intervention or study participation, the investigator must promptly notify the sponsor.

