#### 5.5.5 Adverse Events

A TEAE is defined as any event arising or worsening after first dose study drug until 30 days after last dose. If an AE occurs before the first dose of treatment it will be considered a non-treatment emergent AE.

TEAEs and AEs will be summarized by frequency and percentage of patients and tabulated by MedDRA system organ class (SOC) and preferred term (PT), by maximum NCI-CTCAE version 5.0 grade and by drug relationship as not related and related to treatment. SAEs, TEAEs leading to treatment discontinuation and deaths will be summarized. Drug-related TEAEs by CTCAE grade, and drug-related grade 3 or higher TEAEs are summarized. Patients with multiple TEAEs or AEs are counted once within a summary category-SOC, PT, maximum grade, or relationship to treatments.

AESI be summarized by SOC and PT and grade in separate summary tables. All AEs will be listed.

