### **5.5.6 Laboratory Data**

Laboratory data are summarized by laboratory tests for the treatment period, defined as the time from first dose up to 30 days post last dose of treatment. Laboratory data are converted to SI units prior to summarization. All laboratory tests are provided in patient data listings. The listings indicate the normal ranges for each parameter. Each value, if appropriate, is classified as falling above (H), below (L), or within normal range and also graded using the CTCAE criteria.

The observed data and change from baseline are summarized at each of the laboratory timepoints, using descriptive statistics, for hematology, chemistry and urinalysis laboratory tests.

The changes from baseline to maximum CTCAE grade during treatment are summarized by frequency and percentage of patients using shift tables for every gradable hematology and chemistry tests. Maximum CTCAE Grade is defined as the highest CTCAE version 5.0 grade reported during the treatment period.

A listing of patients with grade 3 or 4 laboratory values during treatment period is also provided.

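### SAP 5.5.5 contradicts itself, and Protocol 8.2, on whether an adverse event that starts before first dose and worsens on drug is treatment-emergent

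*Protocol*

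**What the plan says.** Three rules bear on the start of the treatment-emergent window.

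- Protocol 8.2 defines a TEAE as "any event arising or worsening after start of study drug administration until 30 days after the last study drug intake".
- SAP 5.5.5 begins in the same sense: "A TEAE is defined as any event arising or worsening after first dose study drug until 30 days after last dose".
- The next sentence of SAP 5.5.5 reads: "If an AE occurs before the first dose of treatment it will be considered a non-treatment emergent AE". It does not mention worsening.

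Protocol 8.3.1 ensures that pre-dose events are in the database: "Medical occurrences that begin before the start of study intervention but after obtaining informed consent will be recorded on the AE section of the CRF". SAP 6.0 declares no changes to the planned analyses.

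At the other end, both documents keep the TEAE window open to 30 days after last dose. SAP 5.5.6 uses the same limit for the laboratory treatment period, "defined as the time from first dose up to 30 days post last dose of treatment". Protocol 6.5 states that "another systemic antineoplastic therapy may be initiated no sooner than 7 days after the last dose of study intervention", and has later systemic antineoplastic therapies for prostate cancer recorded. Neither document separates events that occur after such therapy begins.

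**The concern.** A programmer cannot apply both sentences of SAP 5.5.5 to an event that starts before first dose and then worsens on drug. The second sentence is the easier one to code, because it needs only an onset date. SAP 4.2 gives rules for partial AE start dates but none for a date of worsening, which makes the onset-date test the likely default.

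If that happens, real on-drug worsening leaves the TEAE tables. The trial's rationale is a differentiated tolerability profile, and safety against enzalutamide is a secondary objective. Grade 1 fatigue in screening that becomes grade 3 on treatment is the kind of event these tables are meant to show.

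The end of the window raises a smaller question: part of the 30-day tail may be spent on the next cancer drug, and no planned output shows how much that matters.

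**Working it through.** This is mainly a comparison of texts; there is no planned figure to reproduce.

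**Step 1. Apply each rule to the same events.**

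| Event | Protocol 8.2 | SAP 5.5.5, first sentence | SAP 5.5.5, second sentence |
|---|---|---|---|
| Starts after first dose | TEAE | TEAE | Not excluded |
| Starts before first dose, never worsens | Not a TEAE | Not a TEAE | Not a TEAE |
| Grade 1 before first dose, grade 3 on drug, one record | TEAE | TEAE | Not a TEAE |
| Same course, worsening entered as a new AE with on-drug onset | TEAE | TEAE | New record not excluded |

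The rules disagree only in the third row. There the second SAP sentence conflicts both with the sentence before it and with the protocol.

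**Step 2. Length of the exposed period.** This runs from consent at screening to first dose.

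- Lead-in phase: Protocol Table 1–1 places screening "within 21 days prior to first dose", so up to 21 days.
- Randomized phase: Protocol Table 1–2 allows 21 days before randomization and a further 21 days to Week 1 Day 1. 21 + 21 = up to 42 days.

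**Step 3. Outputs affected.** SAP 5.5.5 plans summaries of TEAEs by system organ class, preferred term, maximum grade and relationship; of drug-related TEAEs; of drug-related TEAEs of grade 3 or higher; and of TEAEs leading to discontinuation. In the SAP's lead-in index these correspond to Tables 7, 8 and 9 and Listings 16.2.7.1 and 16.2.7.2.

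SAP 5.5.5 also tabulates AEs without the treatment-emergent restriction and lists all AEs. SAP 5.5.3 does not state that restriction for SAEs or AEs of interest, and neither does lead-in Table 10 (SAEs).

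**Step 4. Size.** The documents give no AE rates, so the number of events in the third row cannot be computed. What one misclassified participant does to a TEAE percentage can be:

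- Randomized phase: about 120 / 2 = 60 per arm; 1 / 60 = 1.7 percentage points.
- Lead-in phase: about 30 participants; 1 / 30 = 3.3 percentage points.

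**Step 5. End of the window.** 30 − 7 = 23 days, and 23 / 30 = 77%. This is the largest possible overlap with new therapy. Day 7 is the earliest permitted start, and the documents do not say when new therapy usually begins.

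**The case against.** **The SAP does include worsening.** A reader might infer that the SAP simply excludes pre-dose events that worsen, against the protocol. The documents do not support that, because the first sentence of 5.5.5 repeats the protocol's rule. The defect is an unresolved contradiction between adjacent sentences.

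**The worsening may be captured anyway.** Protocol Appendix 3 (10.3.1) treats an increase in the frequency or intensity of a pre-existing condition as an AE. If that is entered as a new record with its own onset date, it is a TEAE under every rule. This stands, and it limits the loss to worsening held under one record. It does not remove the problem: Appendix 3 (10.3.3) sends updated information to the form first completed, and the documents do not settle which practice applies to a change of grade.

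**Other tables still show the event.** As planned in SAP 5.5.3 and 5.5.5, grade 1 fatigue that rises to grade 3 would remain in the all-AE and AE-of-interest summaries. This also stands. The reassurance is weaker for the lead-in phase, whose output index names TEAE tables and an SAE table but no all-AE or AE-of-interest table.

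**The 30-day tail.** A reader might also infer that the window is faulty at its end because another drug may start from day 7. The documents do not support that either. Protocol and SAP agree on 30 days, which matches SAE collection and the end-of-treatment visit. TEAE is defined by timing, not cause, and drug-relatedness is tabulated separately. Relatedness is judged by investigators in an open-label trial, so it is only a partial answer. But cutting the main window at the switch would move late effects of study drug out of the main table. That is a trade-off between two defensible choices.

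**Bias between arms.** A reader might go on to infer a spurious difference between arms. The documents give no discontinuation rates, switching rates or AE rates after switching. Any figure would come entirely from assumed differences, and equal rates in both arms would give an expected difference of zero.

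**Conclusion.** The point holds for the start of the window. SAP 5.5.5 gives two incompatible answers for an AE that begins before first dose and worsens on drug, and its second sentence, read literally, is an undeclared departure from Protocol 8.2.

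An event is lost only if three conditions are met: it began between consent and first dose, its worsening is kept under the same record, and the second sentence governs the programming. The loss is then confined to the TEAE outputs. The number of participants is unknown; each one moves a TEAE percentage by about 1.7 points per randomized arm or 3.3 points in the lead-in phase.

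The AE summaries are descriptive and the TUG primary endpoint is untouched, so the consequence is limited. The text is nevertheless wrong as written and should be corrected before database lock.

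The end of the window is not an error. The possible overlap of up to 23 of 30 days justifies, at most, an added sensitivity summary.

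**What to change.** **Needed.** Replace the second sentence of SAP 5.5.5 with: *An AE with onset before first dose is non-treatment-emergent unless its CTCAE grade worsens after first dose.* State alongside it how a change of grade is recorded and dated, whether as a new AE record or as a dated change within the existing one, so that the rule can be programmed. The cost is one clause and a check that the CRF captures the date of worsening.

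**Optional.** Keep the 30-day TEAE window and the 30-day laboratory period in SAP 5.5.6 as the main analysis. Add a sensitivity summary of each that stops at the start of the first new systemic antineoplastic therapy, using the subsequent-therapy records already collected. The cost is a small set of extra tables. Because the main tables are unchanged, late effects of study drug stay in them.

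Neither change alters the 7-day rule, SAE collection or reporting, or any clinical procedure.
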